1. PROJECT TITLE

Yoga for Active Duty Military with CLBP and/or CNP

4. ESTIMATED DURATION OF THE STUDY

Three years.

5. LAY LANGUAGE SUMMARY OR SYNOPSIS (no more than one paragraph)

Our primary aim is to assess the feasibility of conducting yoga research among active-duty military personnel with Chronic Low Back Pain (CLBP) or Chronic Neck Pain (CNP). In addition, we will evaluate the yoga intervention preferences and refine an existing yoga intervention to address those needs. The study will be conducted in two phases: Phase 1 involves collecting qualitative data on the style of yoga that most appeals to military personnel with CLBP, obtaining military IRB approval, and modifying the existing yoga intervention. Phase 2 includes recruitment and randomization of 60 military personnel with CLBP to active yoga or to restorative yoga. This will be conducted at two sites, one at NMCSO and one at Yoga Oceanside. **(Please note: before we begin Phase 2 we will also need to obtain IRB approval from NMCSO for activities that will take place at that site. Once we obtain IRB approval from NMCSO, we will provide a copy to UCSD's IRB prior to commencing any activities at that site.)** Participants will complete assessments at baseline and end of interventions (12-weeks). Phase 1 will be completed over the first 12 months of the 36-month project. Phase 2 will be completed over the remaining 24 months. Pain interference will serve as the primary outcome with physical function and pain severity serving as important additional outcomes. The study will

prepare us for a R01 funded pragmatic clinical trial of yoga for CLBP and CNP in active-duty military.

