6. SPECIFIC AIMS

Phase 1 - includes Aims 1-3 and involves obtaining military IRB approval, using qualitative methods to understand the yoga preferences and attitudes of military personnel with CLBP/CNP, and refining the existing VA yoga intervention to better suit active-duty military personnel.

- Aim 1: Assess and navigate barriers and facilitators for obtaining IRB approval to conduct randomized controlled intervention studies with active-duty military personnel.
- Aim 2: Evaluate the acceptability of and preferences for yoga interventions among active-duty military personnel with CLBP/CNP.
- Aim 3: Modify an existing yoga intervention for the preferences of active-duty military and to address both CLBP and CNP.

Phase 2 –we will accomplish Aims 4-6 by conducting a pilot randomized control trial (RCT) of yoga and a health education self-care control intervention.

- Aim 4: Evaluate the feasibility of recruitment of active-duty military personnel with CLBP/CNP.
- Aim 5: Evaluate adherence to the yoga interventions.
- Aim 6: Obtain effect size estimates to inform power analyses for a full-scale RCT.

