9. RESEARCH DESIGN AND METHODS

Overall

This is a pilot study with an objective to examine the feasibility and acceptability of conducting a yoga RCT among active-duty military personnel with CLBP/CNP in military and community settings. The subject population will consist of 80 adults, 70-75 active-duty military personnel with chronic low back pain (CLBP) or chronic neck pain (CNP) and 5-10 yoga instructors or healthcare providers who have provided yoga or care for active-duty military personnel with CLBP or CNP. The study will be conducted in two phases: Phase 1 will involve obtaining IRB approval to conduct research in military settings, collecting qualitative data from stakeholders on attitudes and preferences for yoga interventions, and refining the existing Yoga for CLBP intervention for the needs of active-duty military and persons with CNP. Phase 2 will recruit and randomize 50 military personnel with CLBP or CNP to either active hatha or restorative yoga. Pain interference, pain severity, physical function, opioid medication use, and mental health outcomes are of primary interest. Mechanisms will also be studied.

Phase 1

Phase 1 includes Aims 1-3 and involves obtaining military IRB approval, using qualitative methods to understand the yoga preferences and attitudes of military personnel with CLBP/CNP, and refining the existing VA yoga intervention to better suit active-duty military personnel.

Aim 1: Assess and navigate barriers and facilitators for obtaining IRB approval to conduct randomized controlled intervention studies with active-duty military personnel. To achieve Aim 1, we will partner with [name] and [name] from the NMCS D as described above. Both [name] and [name] are researchers /clinicians with experience obtaining IRB approval at NMCS D. [name] has a research nurse with experience assembling the required IRB documents. They will work closely with [name] and the UCSD Project Coordinator to meet NMCS D military IRB requirements, starting as soon as the study has been funded. We expect the military IRB approval process to take approximately 6 months to complete. Yoga is not viewed as high risk or experimental given that it has been well studied elsewhere and few adverse events have been documented²¹. However, to be conservative, we have allotted up to 12 months for military IRB approval and Phase I activities can fully proceed under UCSD IRB approval.

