Aim 3: Modify an existing yoga intervention for the preferences of active-duty military and to address both CLBP and CNP. Based on the results of the qualitative interviews, the existing yoga intervention designed for VA patients with CLBP will be refined and adjusted to better fit the preferences of active-duty military personnel with CLBP or CNP. This process will start with the investigators and yoga experts reviewing [name] report of the qualitative results. The team will also independently review a current Yoga for CLBP manual being used by [name], the Cramer et al. manuscript which lists the 14 yoga poses they selected for treating CNP, and other yoga texts. Investigators and experts will then convene at UCSD for an extended afternoon meeting to select of a pool of possible poses. The PI will then work with orthopedic surgeon [name] and yoga expert [name] to propose specific changes to the intervention. The revisions will be presented to the other collaborators for review and additional discussion. Possible examples include a slightly faster pace, adding postures for additional challenge for those with less impairment (yet easily modified to be safe for all), additional attention tasks or imagery, and further trauma sensitivity. All changes and the rationale behind them will be documented.

Phase 2

Please note: before we begin Phase 2 we will also need to obtain IRB approval from NMCS D for activities that will take place at that site. Once we obtain IRB approval from NMCS D, we will provide a copy to UCSD's IRB prior to commencing any activities at that site. In Phase 2 we will accomplish Aims 4-6 by conducting a pilot RCT with 2 yoga interventions. We will recruit 25 people at each of two sites, one in a military medical facility (NMCS D) and one in a community yoga studio (Yoga Oceanside) near a large military base for a total of 50 participants. Once 25 people have been recruited at each site, they will be randomized to attend either active hatha yoga or restorative yoga.

Screening and Inclusion/Exclusion Criteria.

50 active-duty military personnel with CLBP will be recruited and randomized to either active hatha yoga or to restorative yoga. Inclusion criteria are as follows:

Inclusion:

- Diagnosis of CLBP or CNP > 6 months
- Willing to attend a yoga program for 12 weeks
- Willing to complete 3 assessments
- English literacy
- Have had no changes in pain treatments in the past month

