10. HUMAN SUBJECTS

The subject population will consist of 80 adults, 70-75 active-duty military personnel with chronic low back pain (CLBP) or chronic neck pain (CNP) and 5-10 yoga instructors or healthcare providers who have provided yoga or care for active-duty military personnel with CLBP or CNP.

In Phase 1:

30 qualitative interviews will be conducted. 20-25 active-duty military personnel and 5-10 yoga instructors or healthcare providers who have provided yoga or care for active-duty military personnel with CLBP or CNP will participate in the interviews. Inclusion criteria for the qualitative interviews includes being active-duty personnel in the U.S. military, and having a self-reported history of CLBP or CNP. Inclusion criteria for instructors/providers includes having self-reported experience teaching yoga or providing other pain treatments for active-duty military personnel with CLBP or CNP.

In Phase 2: 50 active-duty military personnel with CLBP will be recruited and randomized to either active hatha yoga or to restorative yoga. Inclusion criteria are as follows:

Inclusion:

- Diagnosis of CLBP or CNP > 6 months
- Willing to attend a yoga program for 12 weeks
- Willing to complete 3 assessments
- English literacy
- Have had no changes in pain treatments in the past month
- Willing to not change pain treatments during study unless medically necessary
- Have not practiced yoga more than 2x in the last 12 months

Exclusion:

- Back or neck surgery within the last year
- Back or neck pain due to specific systemic problem (e.g., lupus, scoliosis)
- Severe vertebral disk problems,
- Persistent sciatica or nerve compression > 3 months
- Coexisting chronic pain problem (e.g., migraine headaches, fibromyalgia)
- Serious or unstable psychiatric illness (e.g., psychosis, mania, episode, or substance dependence)
- Major coexisting medical illness (e.g., cancer, COPD, morbid obesity)
- Positive Romberg test (with or without sensory neuropathy)

No other exclusion criteria will be employed. No special classes of subjects or other vulnerable populations will be recruited. We will make efforts to recruit at least representative proportions of women and racial and ethnic minorities. More detail is provided on the inclusion of women and minorities document in this application.

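### The synopsis plans to randomise 60 people in Phase 2, while the design, human-subjects and compensation sections plan 50; the sponsor should confirm one number

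*Combined protocol and SAP*

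**What the plan says.** The synopsis in section 5 gives the larger figure: "Phase 2 includes recruitment and randomization of 60 military personnel with CLBP to active yoga or to restorative yoga".

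The body of the protocol gives the smaller one:

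- Section 9, Overall: "Phase 2 will recruit and randomize 50 military personnel with CLBP or CNP to either active hatha or restorative yoga".
- Section 9, Phase 2: "We will recruit 25 people at each of two sites", with the sum given as "near a large military base for a total of 50 participants". The screening paragraph that follows repeats 50.
- Section 10, Phase 2: "50 active-duty military personnel with CLBP will be recruited and randomized to either active hatha yoga or to restorative yoga".
- Section 20 budgets classes and gift cards for 50 Phase 2 participants.

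Sections 9 and 10 also give totals over both phases: "The subject population will consist of 80 adults, 70-75 active-duty military personnel". Phase 1 is 30 interviews, made up of "20-25 active-duty military personnel and 5-10 yoga instructors or healthcare providers".

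The randomisation paragraph of section 9 (Assessments and Randomization) describes one block file per site with 30 entries in each.

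Section 6 lists recruitment as an aim without a number: "Aim 4: Evaluate the feasibility of recruitment of active-duty military personnel with CLBP/CNP". Section 17 says that the study is not powered for conclusions about efficacy.

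**The concern.** Both figures describe the same quantity, people recruited and randomised in Phase 2. The difference therefore cannot be one between screened and randomised, or between enrolled and completing. No section offers an allowance for dropout or over-recruitment that would link the two.

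The study is a feasibility pilot, and recruitment is one of the things it sets out to evaluate. The planned number is the natural yardstick for describing how recruitment went. If two numbers stand, the final report can be read against either. A trial that randomised between 51 and 60 people would also be within its synopsis but beyond its design, human-subjects and compensation sections.

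**Working it through.** **Inputs.** Synopsis (section 5): 60. Sections 9, 10 and 20: 50. Sites: 2, with 25 each (section 9, Phase 2). Phase 1: 30 interviewees, of whom 20-25 are military (section 10). Totals: 80 adults, 70-75 military (sections 9 and 10). Randomisation files: 30 entries per site (section 9).

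**1. Site split.** 2 x 25 = 50. This reproduces the figure in the body, not the 60 in the synopsis.

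**2. Study totals with no overlap between phases.**

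| Phase 2 number | All adults | Military |
|---|---|---|
| 50 | 30 + 50 = 80 | 20 + 50 = 70 to 25 + 50 = 75 |
| 60 | 30 + 60 = 90 | 20 + 60 = 80 to 25 + 60 = 85 |
| Stated | 80 | 70-75 |

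The row for 50 matches the stated totals exactly; the row for 60 does not.

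**3. Overlap needed to rescue 60.** 90 - 80 = 10 adults; 80 - 70 = 10 and 85 - 75 = 10 military. The totals would hold with 60 only if exactly 10 military interviewees also entered Phase 2. The documents neither allow nor rule out such overlap, so the totals support 50 but do not prove it.

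**4. Randomisation files.** 2 x 30 = 60, which equals the synopsis figure. If 25 per site are planned, each file holds 30 - 25 = 5 entries more than needed. The documents do not say which applies.

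**5. Could 60 be 50 inflated for dropout?** 1 - 50/60 = 0.167, so an allowance of about 17% would turn 50 into 60. No such allowance is stated, and both figures are described as randomised.

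**6. Size of the gap.** 60 - 50 = 10 participants, or 10/50 = 20% of the smaller figure. If 50 were randomised, that would be 50/50 = 100% of one figure and 50/60 = 83% of the other.

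**7. Precision for Aim 6 (illustration).** Assume equal arms, no dropout, and no adjustment for site or covariates. The 95% half-width for a between-group difference, in units of the SD of the quantity compared, is multiplier x sqrt(2/n per arm).

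- N = 50 (25 per arm): sqrt(2/25) = 0.283. Half-width 0.554 with the normal multiplier, 0.569 with t on 48 df.
- N = 60 (30 per arm): sqrt(2/30) = 0.258. Half-width 0.506 with the normal multiplier, 0.517 with t on 58 df.
- Ratio: sqrt(60/50) = 1.095, so the interval is about 10% wider at 50.

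**The case against.** The strongest reply is that this is one number in a one-paragraph lay summary, that the operative sections agree with each other, and that nothing in the plan depends on it. Most of that stands. No power calculation or analysis rule uses the Phase 2 number, and a change of about 10% in interval width triggers nothing. The precision illustration is also simpler than the planned random effects model.

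A reader might infer that Aim 4 has two conflicting recruitment targets, so that the same result could count as success or failure. The documents do not support that. Aim 4 has no number, and no recruitment rate, success threshold or progression rule appears anywhere. The contrast of 100% with 83% is an illustration and changes no decision that the plan defines.

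A reader might also infer that the split of 25 per site proves 60 to be a slip. It does not: the split is one side of the conflict restated by site. The randomisation files point the other way, since two files of 30 make exactly 60, and 30 divides evenly between two arms (15 and 15) where 25 does not. So 60 may be more than an isolated typing error. Equally, the files do not contradict 50, because a list can hold spare entries.

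The reply does not remove the discrepancy itself. No redaction, amendment text or dropout allowance explains it.

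**Conclusion.** The Phase 2 sample size is stated inconsistently: 60 in the synopsis and 50 in sections 9, 10 and 20, a gap of 10 participants. The weight of the text favours 50. It is stated repeatedly, it has a per-site breakdown, and it gives the study totals exactly if no interviewee enters Phase 2. That no-overlap condition is an assumption. The length of the randomisation files is the one other figure that agrees with 60, so the sponsor has to say which number is intended.

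This is a consistency correction to a stated sample size. It is worth making because the number is the implied reference for describing recruitment in a feasibility pilot. It is not evidence of a faulty power calculation, since there is none, nor of an invalid analysis.

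**What to change.** The sponsor should confirm the Phase 2 number and state it identically throughout.

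- **If 50 is intended:** change the synopsis to 50, and add a sentence to the randomisation paragraph of section 9 saying that each 30-entry file includes spare entries beyond the 25 planned per site. This costs one number and one sentence, with no added participants and no change of design.
- **If 60 is intended:** change section 9 (Overall, and both statements under Phase 2), section 10 and section 20 to 60, with 30 per site. If no interviewee enters Phase 2, change the totals in sections 9 and 10 to 90 adults and 80-85 military. This means 10 more participants than those sections now describe and, at the 60 dollars per participant in section 20, 10 x 60 = 600 dollars more in gift cards.

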6. SPECIFIC AIMS

Phase 1 - includes Aims 1-3 and involves obtaining military IRB approval, using qualitative methods to understand the yoga preferences and attitudes of military personnel with CLBP/CNP, and refining the existing VA yoga intervention to better suit active-duty military personnel.

- Aim 1: Assess and navigate barriers and facilitators for obtaining IRB approval to conduct randomized controlled intervention studies with active-duty military personnel.
- Aim 2: Evaluate the acceptability of and preferences for yoga interventions among active-duty military personnel with CLBP/CNP.
- Aim 3: Modify an existing yoga intervention for the preferences of active-duty military and to address both CLBP and CNP.

Phase 2 –we will accomplish Aims 4-6 by conducting a pilot randomized control trial (RCT) of yoga and a health education self-care control intervention.

- Aim 4: Evaluate the feasibility of recruitment of active-duty military personnel with CLBP/CNP.
- Aim 5: Evaluate adherence to the yoga interventions.
- Aim 6: Obtain effect size estimates to inform power analyses for a full-scale RCT.

7. BACKGROUND AND SIGNIFICANCE

Chronic low back pain (CLBP) and chronic neck pain (CNP) are highly prevalent conditions that become chronic in 20-30% of those afflicted.¹ In addition to pain, CLBP and CNP are associated with decreased functional ability,² work absence,^{3,4} increased psychological symptoms, (depression,^{5,6} anxiety^{7,8}) and higher health care costs.⁹ Military personnel^{10,11} and veterans¹² have higher rates of CLBP/CNP than the general US population, and CLBP/CNP are two of the most common reasons for disability among deployed personnel¹¹ and the military in general.¹³ CLBP/CNP in military personnel are often exacerbated by co-morbidities^{14,15} that pose additional challenges and can interfere with treatment. Recommended treatment for CLBP/CNP begins with medication management and self-care instruction,¹⁶ but the limited effectiveness of these approaches and risks associated with pain medication creates a need for non-pharmacologic approaches.^{17,18} Of the non-pharmacological approaches, none have large effects for CLBP/CNP. Because yoga can benefit health much more broadly and has few side effects, it is an increasingly valued care option among military personnel.^{19,20}

Yoga interventions involve the integration of physical postures and movement, deep breathing, and focused attention. Thus, yoga interventions are multifaceted, with documented physical and psychological benefits including a) increased strength, flexibility, and conditioning through the performance of physical postures, and b) stress reduction/ relaxation and improved psychological functioning facilitated by deep breathing exercises, concentration/ attention, and cognitive strategies.

Although the evidence for yoga as a treatment for CLBP was rated as “fair” in 2007 clinical guidelines,¹⁸ two more recent large RCTs provide strong evidence that yoga reduces pain and disability among persons with CLBP.²¹⁻²³ However, none of these studies were conducted in military populations. PI-[name] has conducted preliminary studies showing that VA patients with CLBP/CNP will attend yoga sessions and that yoga improved their pain, physical function, and other outcomes.^{24,25} He is currently finishing a full-scale RCT of yoga for CLBP/CNP in the VA system and collaborates on a similar NCCIH project with [name]. However, military personnel with CLBP/CNP¹⁰ are on average, much different than VA patients with CLBP/CNP²⁶. They are considerably younger and more active, have different co-morbidities and career objectives, and require different treatment strategies. Creating interventions that can treat more than a single condition is also needed. Health organizations cannot easily offer a long menu of yoga interventions, each designed for a specific health condition. Our pragmatic clinical trial approach will address this barrier by designing an intervention to address two common and similar spinal conditions and compare two different styles of yoga in one study.

8. PROGRESS REPORT

N/A

9. RESEARCH DESIGN AND METHODS

Overall

This is a pilot study with an objective to examine the feasibility and acceptability of conducting a yoga RCT among active-duty military personnel with CLBP/CNP in military and community settings. The subject population will consist of 80 adults, 70-75 active-duty military personnel with chronic low back pain (CLBP) or chronic neck pain (CNP) and 5-10 yoga instructors or healthcare providers who have provided yoga or care for active-duty military personnel with CLBP or CNP. The study will be conducted in two phases: Phase 1 will involve obtaining IRB approval to conduct research in military settings, collecting qualitative data from stakeholders on attitudes and preferences for yoga interventions, and refining the existing Yoga for CLBP intervention for the needs of active-duty military and persons with CNP. Phase 2 will recruit and randomize 50 military personnel with CLBP or CNP to either active hatha or restorative yoga. Pain interference, pain severity, physical function, opioid medication use, and mental health outcomes are of primary interest. Mechanisms will also be studied.

Phase 1

Phase 1 includes Aims 1-3 and involves obtaining military IRB approval, using qualitative methods to understand the yoga preferences and attitudes of military personnel with CLBP/CNP, and refining the existing VA yoga intervention to better suit active-duty military personnel.

Aim 1: Assess and navigate barriers and facilitators for obtaining IRB approval to conduct randomized controlled intervention studies with active-duty military personnel. To achieve Aim 1, we will partner with [name] and [name] from the NMCS D as described above. Both [name] and [name] are researchers /clinicians with experience obtaining IRB approval at NMCS D. [name] has a research nurse with experience assembling the required IRB documents. They will work closely with [name] and the UCSD Project Coordinator to meet NMCS D military IRB requirements, starting as soon as the study has been funded. We expect the military IRB approval process to take approximately 6 months to complete. Yoga is not viewed as high risk or experimental given that it has been well studied elsewhere and few adverse events have been documented²¹. However, to be conservative, we have allotted up to 12 months for military IRB approval and Phase I activities can fully proceed under UCSD IRB approval.

Aim 2: Evaluate the acceptability of and preferences for yoga interventions among active-duty military personnel with CLBP/CNP. 30 total Qualitative Interviews will be conducted with military personnel with CLBP or CNP and with healthcare providers who provide yoga or other healthcare to military personnel with CLBP or CNP.

Qualitative Interview Methods:

The proposed qualitative component of the study is both exploratory and inductive in nature. Semi-structured qualitative interviews will be employed to explore the participant preferences and experiences with yoga in relation to their CLBP/CNP. This information will contribute to the refinement of an existing yoga intervention for veterans with CLBP so that it is optimal for active-duty military personnel. Interview techniques will use open-ended questions to stimulate a wider range of responses for a more complete understanding of the needs and attitudes encountered by study participants. Interviews are expected to last about 60 minutes in length. Open-ended questions during the interviews will address: 1) past experiences with non-pharmacological treatments for CLBP/CNP; 2) past experiences with yoga; 3) a brief presentation of the existing yoga program; 4) preferences in regard to the emphasis given to the various components the yoga intervention such as postures, pace of transition through poses, breathing techniques, meditation, ethical principles and spiritual aspects; 5) dosing of yoga; and 6) discussion of research participation and burden given military schedules. Interviews with yoga providers and other health care providers will follow the same set of questions but will ask for both their own preferences as a clinician and their perspective on how their patients

might typically respond. Of the 30 interviews, we will interview 8-10 participants with CLBP/CNP who have never done yoga. Those interviews will employ slightly different questions that are designed to elicit attitudes, beliefs, and perceptions about yoga as a treatment modality for CLBP/CNP in military personnel, and barriers to participation. Instead of a question about their past experiences with yoga, they will be asked to provide their perceptions of yoga as a treatment modality and any barriers or facilitators that may affect their future participation. All qualitative interviews will be digitally audio-recorded and digital tapes will be encrypted before being confidentially submitted to a transcription consultant to transcribe the audio recordings verbatim for the purpose of coding and analysis. All names and locations mentioned during the course of the interviews will also be removed from the final transcripts prior to analysis.

Qualitative Data Analysis:

A salient strength of qualitative analysis is its focus on the context and meaning of human experience for the purpose of inductive and exploratory-driven research. Qualitative methods facilitate the collection of data when exact measures do not exist. Transcribed summaries from the interviews will be analyzed using directed content analysis (DCA) to identify and categorize meaningful and detailed information about participant's opinions, perceptions and experiences participating in the mindfulness meditation intervention. Coding strategies will include highlighting passages for emergent themes and also a priori categories reflecting questions from the interviews. Through this process and the comparison of new data, a template of open codes will be constructed to analyze all of the transcripts in accordance with standard qualitative analytic convention. Verification of emergent themes from interviews will be examined through investigator discussions of the coding framework. Disagreements during theme interpretation or coding hierarchy will be resolved early on through investigator discussions before completing the qualitative analysis.

Aim 3: Modify an existing yoga intervention for the preferences of active-duty military and to address both CLBP and CNP. Based on the results of the qualitative interviews, the existing yoga intervention designed for VA patients with CLBP will be refined and adjusted to better fit the preferences of active-duty military personnel with CLBP or CNP. This process will start with the investigators and yoga experts reviewing [name] report of the qualitative results. The team will also independently review a current Yoga for CLBP manual being used by [name], the Cramer et al. manuscript which lists the 14 yoga poses they selected for treating CNP, and other yoga texts. Investigators and experts will then convene at UCSD for an extended afternoon meeting to select of a pool of possible poses. The PI will then work with orthopedic surgeon [name] and yoga expert [name] to propose specific changes to the intervention. The revisions will be presented to the other collaborators for review and additional discussion. Possible examples include a slightly faster pace, adding postures for additional challenge for those with less impairment (yet easily modified to be safe for all), additional attention tasks or imagery, and further trauma sensitivity. All changes and the rationale behind them will be documented.

Phase 2

Please note: before we begin Phase 2 we will also need to obtain IRB approval from NMCS D for activities that will take place at that site. Once we obtain IRB approval from NMCS D, we will provide a copy to UCSD's IRB prior to commencing any activities at that site. In Phase 2 we will accomplish Aims 4-6 by conducting a pilot RCT with 2 yoga interventions. We will recruit 25 people at each of two sites, one in a military medical facility (NMCS D) and one in a community yoga studio (Yoga Oceanside) near a large military base for a total of 50 participants. Once 25 people have been recruited at each site, they will be randomized to attend either active hatha yoga or restorative yoga.

Screening and Inclusion/Exclusion Criteria.

50 active-duty military personnel with CLBP will be recruited and randomized to either active hatha yoga or to restorative yoga. Inclusion criteria are as follows:

Inclusion:

- Diagnosis of CLBP or CNP > 6 months
- Willing to attend a yoga program for 12 weeks
- Willing to complete 3 assessments
- English literacy
- Have had no changes in pain treatments in the past month

- Willing to not change pain treatments during study unless medically necessary
- Have not practiced yoga more than 2x in the last 12 months

Exclusion:

- Back or neck surgery within the last year
- Back or neck pain due to specific systemic problem (e.g., lupus, scoliosis)
- Severe vertebral disk problems,
- Persistent sciatica or nerve compression > 3 months
- Coexisting chronic pain problem (e.g., migraine headaches, fibromyalgia)
- Serious or unstable psychiatric illness (e.g., psychosis, mania, episode, or substance dependence)
- Major coexisting medical illness (e.g., cancer, COPD, morbid obesity)
- Positive Romberg test (with or without sensory neuropathy)

No other exclusion criteria will be employed. No special classes of subjects or other vulnerable populations will be recruited. We will make efforts to recruit at least representative proportions of women and racial and ethnic minorities. More detail is provided on the inclusion of women and minorities document in this application.

Inclusion Criteria	Determined by:	Exclusion Criteria	Determined by:
Active-duty military employment and age ≥ 18	screening interview; medical record	back or neck surgery within the last 1 year	screening interview; medical record
Diagnosis of chronic low back or neck pain > 6 months	screening interview; medical record	back or neck pain due to specific systemic problem (e.g., lupus)	screening interview; medical record
Willing to attend 12-weeks of yoga	screening interview; informed consent	severe vertebral disk problems	screening interview; medical record
Willing to complete 2 assessments	screening interview; informed consent	persistent sciatica or nerve compression > 3 months	screening interview; medical record
English Literacy	screening interview; informed consent	coexisting chronic pain problem (migraine headaches, fibromyalgia)	screening interview; medical record
No changes in pain treatments in the past month.	medical record; screening interview	Serious or unstable psychiatric illness (e.g. psychosis, mania)	screening interview; medical record
Willing to not change pain treatments during study unless medically necessary.	screening interview; informed consent	major coexisting medical illness (e.g., cancer, COPD, morbid obesity)	screening interview; medical record
Have not practiced yoga > 2x in the last 12 months	screening interview; informed consent	Positive Romberg test (with or without sensory neuropathy)	screening interview; medical record

Recruitment staff will meet with participants to obtain informed consent and HIPAA authorization before a screening visit. Potential participants will undergo a physician screening exam to ensure they meet the study inclusion/exclusion criteria and can participate safely. Screening will be performed by [name] at NMCSO or by [name] at UCSO for the community site and includes a review of the patients’ medical record, a brief interview, and a physical examination. Inclusion/ exclusion criteria and the sources of information used to determine them are listed in Table 4. Patients who have recently changed any professionally-delivered pain treatment (e.g., medications, chiropractic) are not eligible until their treatment has been stable for 30 days. Participants are asked to keep all pain treatments stable during the 12-week intervention period unless a change is medically necessary and their agreement and study participation are documented in their medical record. Staff will assess all treatments including non-prescription medication use and any treatment changes that do occur through self-report assessment at 4-weeks, 8-weeks, and the end of the 12 week study period. Participants are asked take their lowest usual dose of pain medications within 24 hours of each assessment. Although we will exclude those with serious or unstable psychiatric illness, we expect to enroll many patients with stable levels of depression, anxiety (including PTSD), substance use, etc. as these conditions are prevalent and contribute to disability among CLBP/CNP patients. Research suggests that yoga has beneficial effects on psychiatric symptoms. We will exclude patients who report active suicidal ideation at baseline or have recent suicide attempts.

Assessments and Randomization:

All eligible participants will be scheduled for assessments at two time points: pre (baseline) and post intervention (12-weeks). The assessments consist of a battery of 8-10 questionnaires taking about 20-30 minutes to complete. Next, physiological measurements will be conducted by a trained research assistant and will take about 10 minutes to complete. Participants will receive \$30 for completing each assessments. Completed questionnaires will be coded with a study ID to protect confidentiality. All personal health information will be entered into a password protected secure server environment within UCSD-HSRC. After the baseline assessment, participants will be randomized to either the Hatha Yoga Intervention or to the Restorative Yoga Intervention. Randomization will occur through a web portal linked to a secure file providing block randomized digits that was prepared by the study statistician. There will be one block file for each site, with 30 digits in each file, allowing each site to have a balanced randomization. Research staff will not have access to the randomization file. Participants will be told of their group assignment and will be allowed to ask additional questions at that time.

Assessment Questionnaires and Measurements:

Screening: Medical record information will be used by screening physicians to complete the Back Pain History Questionnaire which will allow the investigators to assign a descriptive diagnosis based on the Quebec Nomenclature on Activity Related Spinal Disorders¹⁰⁴. The measure has been used in previous VA studies¹⁰⁵⁻¹⁰⁷. Additional information on co-morbid diagnoses, opioid pain medication usage, and ongoing treatments will also be collected including information on TBI, PTSD and other psychological diagnoses, and substance use.

Demographics: A brief questionnaire will assess age, gender, education, race/ethnicity, employment status, military rank and duties, and combat status.

Pain interference with daily function and pain severity will be measured with the short version of the Brief Pain Inventory (BPI).¹⁰⁸ Pain interference will serve as the primary outcome. The BPI has been validated with CLBP.¹⁰⁹ The pain interference score is the mean of the 7 interference items. The pain severity score is the mean of 4 severity items. The BPI has good reliability (alpha 0.77 - 0.91).

Disability/Physical Function. The Roland-Morris Disability Questionnaire consists of 23 questions that ask about limitations experienced for a variety of daily activities. The scale has been shown to be reliable and is well validated¹¹⁰. It has been used in other studies of yoga studies¹⁰². The Neck Disability Index will be used to assess disability related specifically to neck pain. It is a well validate measure.¹¹¹

Depression. Derived from the full Center for Epidemiologic Studies Short Depression Scale¹¹² (CES-D), the CES-D 10¹¹³ consists of 10 items on the frequency of mood symptoms. Scores ≥ 10 indicate depression.

Anxiety. The Brief Anxiety Inventory (BAI) measures the severity of anxiety symptoms and consists of 21 items. The BAI was developed with psychiatric outpatients¹¹⁴ and has good reliability and validity.¹¹⁵

HRQOL. The Short-form 12 (SF12) was derived the SF-36.¹¹⁶ The PCS-12 and MCS-12 have been shown to be similar to the SF36 levels of precision and sensitivity to change.

Self-efficacy. Self-efficacy for managing pain reflects confidence in the ability to influence the intensity or impact of CLBP/CNP on daily life. The questions are based on items developed by Lorig et al.¹¹⁷.

Fatigue. The Fatigue Severity Scale (FSS) assesses the impact and severity of fatigue with 9 items. A score of ≥ 4.0 constitutes severe fatigue.¹¹⁸ The measure has good psychometrics for pain disorders.^{118,119}

Attendance/ Home practice. Attendance of yoga sessions will be assessed using sign-in logs verified by the yoga instructor. Self-reported practice of yoga at home will be assessed using a weekly participant yoga log. The yoga log assesses the amount of time practiced, the use of instructions, the difficulty of poses, and the estimated level of exertion.

Acceptability and Satisfaction Questions. We will assess program acceptability and satisfaction using 10 questions developed and used by the investigators in previous and current yoga studies. The questions will gauge factors affecting attendance and participation levels.

Patient Expectations will be measured at baseline to determine whether the descriptions of the yoga interventions could result in different expectations for improvement. [name] will use the new patient expectation measure developed by her and her colleagues.¹²⁰

